Baseline Data Collection Following consent, young adult participants will be enrolled in the study and emailed a link and login information to access a password-protected web portal on a secure, HIPAA-compliant server operated through the BCM Clinical Trials Management System, where they will complete baseline questionnaires (see Combined Measures attachment in Section S). To facilitate retention, we will ask participants to provide their contact information, contact information for family/friends who could put us in touch with them if we cannot make follow-up contact, and social media handles for us to contact them via study accounts on social media platforms if we cannot make follow-up contact by any other method.

Upon enrollment, participants will complete a HbA1c dried blood spot at-home test kit if a recent POC or lab drawn value is not available. Each participant will receive a packet by mail which will have all necessary supplies, instructions, and a self addressed prepaid mailer to return to study staff. In order to provide the blood spot, the participant will need to do a finger poke using the lancet provided within the test kit. The blood collection lancet is an FDA 510K cleared device, which is what the patient

will use to poke their finger and collect the blood on the paper. This lancet is designed to provide a deeper finger poke in order for the participant to draw enough blood to fill 3 of the 5 small half inch circles on the blood spot card. This lancet may cause brief discomfort in the finger of the participant. Each participant will be instructed to wash their hands, warm their finger either by rubbing or with warm water, and then clean the finger to be used with an alcohol pad and dry well. They will then poke their finger with the spring loaded lancet and count to 2 before removing. Next, they will wipe away the first drop of blood and then apply gentle pressure and allow a drop of blood to fall on 3 of the small half inch circles. The drop of blood should soak through the card and then the participant will need to air dry the card for 3 hours. Each circle can hold up to 75 to 80 μ L of blood. The test itself is cleared by the FDA as a moderately complex test (under lab test regulations). The blood spot cards we will be utilizing (Whatman 903 cards) are approved by the FDA as Class II devices. The HbA1c on filter paper is extracted and measured on the Vitros 4600 HbA1c assay. This assay is correlated with the DCA 2000.

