As a supplement to HbA1c, we will also collect continuous glucose data, as recommended by recent consensus guidelines to measure glycemic control with measures beyond HbA1c. We will collect these data directly from participants who are using a continuous glucose monitor (CGM) device. We will collect 14 days of raw data and summary variables (e.g., estimated average glucose, percent time in target glucose range) using cloud-based data platforms either from the manufacturer (e.g., Dexcom Clarity) or using the Texas Children's Hospital healthcare professional access (e.g., Glooko). To use manufacturer platforms, participants will be asked to follow the platform's process to grant data access to study staff via a 12-month code. This is the same process patients use to share CGM data with clinical providers as part of usual care. We will collect data at the same timepoints we are collecting other glycemic control data: baseline and 12 months. We will not collect glucose data for any participant not currently using CGM.

Randomization Participants will be randomized upon completion of baseline questionnaires and return of a completed home A1c kit to intervention or usual care in a 1:1 ratio using a permuted block design. The intervention will begin that day and take place for 12 months.

Peer Mentor Recruitment Peer Mentors will deliver the intervention and will also be enrolled as study participants to permit assessment of their own outcomes. Peer Mentors will be experienced young adults with T1D who have transferred to adult diabetes care. Potential Peer Mentors will be recruited through referrals from previous pediatric providers at TCH, via advertisements in local adult diabetes care centers including BCM (with the support of [name], Co-I), local chapters of the College Diabetes Network, local diabetes group newsletters, and social media. Interested Peer Mentors will be screened for eligibility and interest. Peer Mentors will provide informed consent prior to completing questionnaires and being trained.

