How many subjects (or specimens, or charts) will be used in this study?

Local: 186 Worldwide: 186

Please indicate why you chose the sample size proposed:

We plan to enroll 150 young adult participants and up to 36 peer mentor participants (totaling 186 participants).

Sample Size and Power. A difference of 0.5 percentage points (e.g., reduction in HbA1c from 8.5% to 8.0%) is considered a clinically important difference in HbA1c. A sample size of 128 participants (64 per group) would be required to detect a 0.5 percentage point difference in mean HbA1c between treatment arms using an independent two-sample t-test assuming equal variances, common SD=1, and two-sided $\alpha=0.05$. Therefore, this study will plan to enroll and randomize 150 young adult participants (75/group) to allow for a conservative estimate of 15% attrition based on retention rates ranging between 86-96% in our previous intervention studies.

We will enroll up to 15 advisory board members. We are not collecting data from them so they are not included in sample size and power.

SUPPLEMENT ACTIVITIES SAMPLE SIZE: We plan to invite up to 35 young adult participants to complete the additional follow-up data collection. All participants for the Supplement Activities will be existing participants in the parent trial - there will be no new enrolled participants for the Supplement Activities.

G2. Data Analysis

Provide a description of your plan for data analysis. State the types of comparisons you plan (e.g. comparison of means, comparison of proportions, regressions, analysis of variance). Which is the PRIMARY comparison/analysis? How will the analyses proposed relate to the primary purposes of your study?

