Data Analysis Plan. Baseline demographics and clinical characteristics will be summarized by means with standard deviations, medians with minimum and maximum values, or frequencies with percentages. Summary statistics will be stratified by treatment arm and compared between groups using two-sample t-tests, Wilcoxon rank sum tests, or Fisher's exact tests. Approximate normality for continuous measures will be assessed using quantile-quantile plots and Shapiro-Wilks tests. Departures from normality will be addressed by data transformation (e.g., natural logarithm), categorization, or non-parametric analysis. Statistical significance for the univariable analysis will be assessed at the two-sided 0.05 level; however, significant differences between treatment arms must be due to chance since this is a randomized clinical trial. Missing data on questionnaires are expected to be minimal based on high follow-up data completion rates in preliminary intervention studies and <1% missing item responses in our preliminary study with a similarly-aged sample of young adults. Measures will be scored according to published instructions including rules for handling missing item responses. SAS v9.4 (Cary, NC) will be used for all data summaries and analysis. Aim 1: The primary outcome measure of interest is 12-month HbA1c. An independent, two-sample t-test will be used to compare mean HbA1c between study arms at the 12-month time point. An F test will be used to test the null hypothesis that the variances are equal, and approximate normality will be assessed using QQ-plots and the Shapiro Wilks test. Departures from model assumptions will be addressed by data transformations (e.g., natural logarithm), categorization, or alternative methods of analysis such as Welch's t-test approximation or the Wilcoxon rank sum test. Statistical significance will be assessed at the 0.05 level (2-sided). A general linear mixed model will be used to compare mean HbA1c between study arms after adjusting for baseline HbA1c and other clinically relevant covariates. Parameter estimates for the regression model will be assessed at the 0.05 level of significance (2-sided). Secondary outcomes include the time to first adult care visit, treatment adherence, and quality of life. The time to first adult care visit will be compared between treatment arms using the log-rank test statistic for comparing Kaplan-Meier curves. Time will start on the date of the last pediatric care visit. The event of interest is the date of the first adult care visit. Participants who do not follow-up with an adult care provider within 12 months of the last pediatric visit will be censored for the event at the 12-month time point. The log-rank test statistic will be assessed at the two-sided 0.05 level of significance. A Cox Proportional Hazards

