Audio recordings only identified by study ID may be kept on BCM's Microsoft OneDrive (requires login) temporarily. OneDrive's study folders will only be accessible by study staff. Recordings will be transferred to BCM secure server study share drive folders on a regular basis by study staff. BCM Clinical Trials Management System (CTMS) will be utilized for survey data collection and other study related forms.

Participant addresses will be entered into BCM's Microsoft OneDrive without any identifying information for geocoding.

Will there be anyone besides the PI, the study staff, the IRB and the sponsor, who will have access to identifiable research data?

Yes, identify the classes of the persons:

Audio-recorded interviews with study participants (e.g., satisfaction interviews upon study completion) may be transcribed by medical transcriptionists (we use Landmark Associates) We will collect Hemoglobin A1c data from all participants at two timepoints in the study. These results will be entered into each participant's electronic medical record (EPIC) at Texas Children's Hospital in order to share this data with the participant's medical provider. Due to the COVID pandemic, many patients in the Diabetes Care Center at Texas Children's Hospital have not completed a recent A1c so we are sharing this data.

Please describe the methods of transmission of any research data (including PHI, sensitive, and non-sensitive data) to sponsors and/or collaborators.

We don't anticipate any transmission of research data (sensitive or non-sensitive) with collaborators outside of BCM with a few exceptions noted below. If non-sensitive information is shared with outside institution collaborators, data will be identified before transmission and sent via secure email or via BCM's Microsoft OneDrive. The only exceptions are sharing addresses through OneDrive with Co-I [name] for geocoding and if we get audio-recorded interviews transcribed by medical transcriptionists - we make every effort to not use patient names in the interviews, but occasionally the participant will disclose their name or other PHI in the audio-recorded interviews.

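### The implied primary test of 12-month HbA1c ignores a baseline HbA1c obtained before randomization; adjusting for it would gain power and precision if the two values are correlated

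*Combined protocol and SAP*

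**What the plan says.** Section G2 (Aim 1) makes 12-month HbA1c the primary outcome and gives two analyses of it, both at two-sided 0.05.

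- The first is unadjusted: "An independent, two-sample t-test will be used to compare mean HbA1c between study arms at the 12-month time point". Its fallbacks follow: "Departures from model assumptions will be addressed by data transformations (e.g., natural logarithm), categorization, or alternative methods of analysis", with Welch's test and the Wilcoxon rank sum test as examples.
- The second is a general linear mixed model comparing the arms "after adjusting for baseline HbA1c and other clinically relevant covariates". The other covariates are not named.

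The form asks "Which is the PRIMARY comparison/analysis", and the text does not answer in words. The sample size in section G1 was derived "using an independent two-sample t-test assuming equal variances, common SD=1, and two-sided" 0.05, which points to the t-test as the intended primary analysis.

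On the baseline value, section F2 (Baseline Data Collection) says that "participants will complete a HbA1c dried blood spot at-home test kit if a recent POC or lab drawn value is not available". Its Randomization paragraph says: "Participants will be randomized upon completion of baseline questionnaires and return of a completed home A1c kit". Section K adds: "We will collect Hemoglobin A1c data from all participants at two timepoints in the study". The first two statements differ on whether everyone needs a home kit, but under either one the baseline HbA1c exists before allocation.

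**The concern.** A covariate measured before randomization can be adjusted for without biasing the comparison of arms. If it predicts the outcome, adjustment removes variance that the t-test leaves in the error term. The implied primary analysis therefore gives a wider confidence interval and less power than the collected data allow. Section G2 already adjusts adherence and quality of life for their baseline values; only the primary outcome leads with an unadjusted test.

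The lack of ranking adds to this. Two tests of the same outcome, each at 0.05, can disagree, and the plan does not say which one decides.

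**Working it through.** **Inputs.** From section G1: difference 0.5 percentage points, common SD 1, two-sided alpha 0.05, 64 evaluable per arm (128 in total), 75 randomized per arm (150 in total), 15% attrition. From section F2: 1:1 allocation. Assumed, because the documents do not give it: the correlation ρ between baseline and 12-month HbA1c, taken from 0 to 0.7.

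**Step 1: the plan's own figure.** For a two-sample t-test, the noncentrality is δ / (SD × √(2/n)) = 0.5 / (1 × √(2/64)) = 0.5 / 0.1768 = 2.828, with 2n − 2 = 126 degrees of freedom. Power from the noncentral t distribution is 80.1%. With 63 per arm it is 79.5%, so 64 is the smallest size that reaches 80%. The plan states no power. Of the alternatives tried, two-sided 85% needs 146 in total, two-sided 90% needs 172, and one-sided 80% needs about 100 (50 per arm by the normal approximation), so two-sided 80% is the match. Attrition: 128 / 0.85 = 150.6, against 150 planned. The sample size reproduces.

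**Step 2: adjust for baseline HbA1c.** HbA1c is collected only at baseline and 12 months. The planned mixed model with baseline as a covariate therefore reduces to a linear model (ANCOVA) of one follow-up value. Formulas:

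- residual SD = √(1 − ρ²)
- noncentrality = 0.5 / (residual SD × √(2/64)), with 125 degrees of freedom
- 95% CI half-width = t(0.975) × residual SD × √(2/64), with t(0.975) = 1.979

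At ρ = 0.5, for example, the residual SD is √0.75 = 0.866, the noncentrality is 0.5 / (0.866 × 0.1768) = 3.27, and the half-width is 1.979 × 0.866 × 0.1768 = 0.303.

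| Analysis | Residual SD | Power | Power, allowing for chance baseline imbalance | CI half-width (points) | Detectable difference at 80% power |
|---|---|---|---|---|---|
| t-test | 1.000 | 80.1% | n/a | 0.350 | 0.499 |
| adjusted, ρ = 0 | 1.000 | 80.1% | 79.8% | 0.350 | 0.499 |
| adjusted, ρ = 0.1 | 0.995 | 80.5% | 80.2% | 0.348 | 0.497 |
| adjusted, ρ = 0.2 | 0.980 | 81.7% | 81.4% | 0.343 | 0.489 |
| adjusted, ρ = 0.3 | 0.954 | 83.7% | 83.4% | 0.334 | 0.476 |
| adjusted, ρ = 0.5 | 0.866 | 90.0% | 89.8% | 0.303 | 0.432 |
| adjusted, ρ = 0.7 | 0.714 | 97.6% | 97.5% | 0.250 | 0.356 |

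The imbalance column multiplies the variance of the arm effect by 1 + F/126, where F has 1 and 126 degrees of freedom, and averages power over F. Half-widths and detectable differences do not include this small factor.

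**Step 3: simulation check.** With 20,000 trials per setting and 64 per arm, adjusted power was 83.6%, 89.7% and 97.5% at ρ = 0.3, 0.5 and 0.7. The t-test stayed at 80% to 81%. Type I error was near 5% for each test taken alone.

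**Step 4: cost of leaving the two tests unranked.** If success could be claimed on either test, the simulated type I error would be 6.4%, 7.2% and 8.3% at ρ = 0.3, 0.5 and 0.7. With a true 0.5-point effect, the share of trials in which the tests disagree is 2 × P(either significant) − P(t-test significant) − P(adjusted significant):

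- ρ = 0.3: 2 × 0.856 − 0.805 − 0.836 = 0.07
- ρ = 0.5: 2 × 0.912 − 0.805 − 0.897 = 0.12
- ρ = 0.7: 2 × 0.979 − 0.808 − 0.975 = 0.17

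**The case against.** The strongest reply is that nothing is wrong. The t-test is valid, the trial was sized for it, and an adjusted estimate will be reported anyway. This stands as far as it goes: the point concerns efficiency, and the loss is confined to which analysis decides.

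The second reply is that the gain rests on a correlation the documents do not give. This also stands. Two features could make the correlation low. Baseline may be a point-of-care value, a laboratory value or a dried blood spot. The gap to the outcome may also exceed 12 months, because section F1 enrols at or before the anticipated final pediatric visit and follows participants for 12 months after they leave pediatrics. At 0.1 or 0.2 the gain is negligible. Either feature would shrink the gain; neither would bias the randomized comparison.

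Third, the model proposed here is not exactly the planned one, which has further covariates, and naming the t-test as primary would settle the ranking equally well. Both are true. The proposal is the planned model limited to its one named covariate. The case for preferring it to the t-test is power, not the ranking.

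Last, moving the fallbacks to the t-test leaves the new primary model without a stated answer to unequal variances or non-normality. That is fair, and the fix below allows for it.

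**Conclusion.** The concern holds as a recommended improvement, not as an error in the trial. The implied primary analysis is valid but leaves precision unused if baseline and 12-month HbA1c are correlated. On the plan's figures, adjustment adds about 4 power points at a correlation of 0.3 (83.7% against 80.1%), 10 at 0.5 and 17 at 0.7, and narrows the interval from ±0.35 to ±0.33, ±0.30 and ±0.25 points. The worst case, zero correlation, costs about 0.3 power points.

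These figures assume 64 evaluable per arm, SD 1, normal errors, constant residual variance and a linear relation to baseline. The correlation is an assumption throughout. The balance of gain and cost favours adjustment without needing to know it.

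**What to change.** In section G2 (Aim 1), state: 'The primary analysis is a linear model of 12-month HbA1c on study arm and baseline HbA1c. The arm effect is tested once at two-sided 0.05 and reported with a 95% CI.'

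Label as supportive:

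- the unadjusted t-test, with its transformation, categorization, Welch and Wilcoxon fallbacks;
- the model with further covariates, each named before the data are analysed.

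If protection against unequal variances is wanted in the primary model, name one method in advance, for example heteroscedasticity-consistent standard errors. Keep 150 participants, since the gain is not assured.

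The cost is protocol and analysis-plan wording, with no new data, visits or participants. Because this changes which analysis decides, record it in a dated amendment before 12-month outcomes are seen by arm.

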
regression model will also be used to estimate the Hazards Ratio (95% confidence interval) for adult care follow-up in the intervention versus control groups. Treatment adherence and quality of life will be analyzed using separate general linear mixed models to compare means between study arms over time. The models will include fixed effects for baseline measure, time (6 vs. 12 months), study arm, and the time-arm interaction term. Adherence and quality of life will be analyzed by separate models. Each model will be used to simultaneously compare mean adherence and quality of life measures at the 6- and 12-month time points adjusting for baseline values. Statistical significance will be assessed at the 0.05 level for all secondary hypothesis tests. Aim 2: Regression analysis will be used to test for mediation between study arm and the primary (HbA1c) and secondary outcomes (time to first adult care visit, adherence, quality of life) at 12 months. The 4-step approach recommended by Baron and Kenny¹⁰⁵ will be used to assess transition readiness, perceived support, diabetes strengths, diabetes distress, and depressive symptoms at 6 months as mediators for each outcome. Indirect effects will be assessed by computing the difference between two regression coefficients^{106,107}. Standard errors will be estimated using Bootstrapping. Aim 3: Changes in Peer Mentors' self-report outcome measures will be assessed using paired t-tests or the Wilcoxon signed rank test. Statistical significance will be assessed at the 0.05 level of significance (2-sided). General linear mixed models may also be used to test the association between changes in measures over time with demographic and clinical characteristics. The models will include time (baseline vs. follow-up), covariates, and the covariate-time interaction term. The matrix of correlated residuals will assume an unstructured format.

SUPPLEMENT ACTIVITIES DATA ANALYSIS: We will conduct descriptive statistics (means with standard deviations, medians with minimum and maximum values, or frequencies with percentages) and basic correlations between variables of interest. We will use NVivo software to code qualitative transcripts and conduct hybrid thematic analysis.

Section H: Potential Risks/Discomforts

H1. Potential Risks/Discomforts

Describe and assess any potential risks/discomforts; (physical, psychological, social, legal, or other) and assess the likelihood and seriousness of such risks:

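### Aim 2 names no baseline covariates in its mediation regressions, so a scale that the intervention shifts can appear to mediate an outcome it does not affect

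*Combined protocol and SAP*

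**What the plan says.** Section G2, Aim 2, plans regression-based mediation for HbA1c, adherence, quality of life and the time to a first visit in adult care, at 12 months. The Baron and Kenny four-step approach "will be used to assess transition readiness, perceived support, diabetes strengths, diabetes distress, and depressive symptoms at 6 months as mediators for each outcome". The indirect effect is the difference between two regression coefficients, and its standard error is bootstrapped. No covariate is listed.

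Elsewhere in G2, baseline is used. The supporting mixed model for HbA1c adjusts for baseline HbA1c and other clinical covariates. For adherence and quality of life, "The models will include fixed effects for baseline measure, time (6 vs. 12 months), study arm, and the time-arm interaction term". Nothing carries these terms over to Aim 2, and nothing says they are to be left out.

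Section F2 sends participants to a web portal "where they will complete baseline questionnaires". The list of measures is in an attachment that is not available here.

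**The concern.** Randomization makes the arm-to-mediator and arm-to-outcome comparisons fair. It does nothing for the mediator-to-outcome association, because nobody is randomized to a 6-month score. If participants who enter with more distress or less support also enter with worse HbA1c, adherence or quality of life, and both persist, the 6-month score will predict the 12-month outcome without any causal link. The difference in coefficients turns that association into an indirect effect as soon as the arm shifts the scale.

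That is not a remote case. The intervention described in F2 teaches strengths-based skills and stress management and helps participants draw on their social support, so it is meant to move several of these scales. At stake is the trial's explanation of how the intervention works. The between-arm comparisons in Aim 1 are not affected.

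**Working it through.** **Sample size used.** Section G1 states: "A sample size of 128 participants (64 per group) would be required to detect a 0.5 percentage point difference in mean HbA1c", with SD 1 and two-sided alpha 0.05. Power is not stated. A two-sample t-test at 80% power needs 63.8 per arm, so 64, and 64 per arm gives 80.1%. For 15% attrition, 128 / 0.85 = 150.6, against 150 planned (150 × 0.85 = 127.5). The figure reproduces. Aim 2 has no sample size of its own, so 64 per arm is used below.

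**Assumed inputs (none is in the documents).** Standardized scores; baseline mediator-outcome correlation ρ; correlation k of each score with its own baseline; arm effect a on the mediator and c on the outcome; true effect of mediator on outcome = 0. The main model is autoregressive: M6 = k·M0 + a·Arm + error and Y12 = k·Y0 + c·Arm + error.

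**Expected bias.** In linear regression the difference in arm coefficients equals a·b, where b is the mediator coefficient given arm. Without baselines, b has expectation k²ρ although its true value is 0. The spurious indirect effect is therefore a·k²ρ:

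- ρ = 0.3, k = 0.6, a = 0.5: 0.5 × 0.36 × 0.3 = 0.054 SD
- ρ = 0.5, k = 0.7, a = 0.5: 0.5 × 0.49 × 0.5 = 0.12 SD
- ρ = 0.6, k = 0.7, a = 0.5: 0.5 × 0.49 × 0.6 = 0.147 SD (simulated 0.141)

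Against an outcome effect of 0.5 SD, the simulated range of 0.054 to 0.141 SD is 11% to 28% of the total effect.

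**How often mediation is declared.** Simulated trials, 64 per arm, a = c = 0.5. "Three tests" means that arm-to-outcome, arm-to-mediator and mediator-to-outcome are all significant, which are the significance steps of the four-step rule. "Bootstrap SE" means the indirect effect divided by its bootstrap standard error exceeds 1.96 in absolute value.

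| ρ | k | Mean indirect effect, no baselines | Three tests: none / both baselines | Bootstrap SE: none / both baselines |
|---|---|---|---|---|
| 0.3 | 0.5 | 0.035 | 7.5% / 3.7% | 1.7% / 1.2% |
| 0.3 | 0.7 | 0.073 | 25% / 4.7% | 12% / 1.7% |
| 0.5 | 0.7 | 0.119 | 52% / 4.5% | 38% / 2.3% |

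Over ρ = 0.3 to 0.6 and k = 0.6 to 0.7, the rates without baselines run from about 12% to 60% (three tests) and about 6% to 55% (bootstrap SE). With both baselines they are about 2% to 6%.

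**Which conditions the bias needs** (ρ = 0.5, k = 0.7, no baselines):

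- Arm does not move the mediator: b is still 0.24, but the mean indirect effect is −0.002. The three tests pass in 3% or fewer of trials, and the bootstrap SE test in 1.5%.
- Arm moves the mediator by 0.5 SD but not the outcome: three tests 3%, bootstrap SE 38%.
- Smaller effects, 0.3 SD on both: three tests about 3% to 18% over the ranges above.

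**How far adjustment helps.** If the baselines are imperfect measures of a stable trait, adjustment does not remove everything. With a = c = 0.5, the three-test rate falls from 25%–66% to 5%–12%, and the mean indirect effect from 0.07–0.17 to 0.02–0.04 SD.

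**The case against.** The strongest reply is that the plan is silent, not wrong. A reader might infer that Aim 2 deliberately drops the baselines. The text does not say so: it lists no covariates and excludes none, and its authors adjust for baseline elsewhere in G2. That stands, and the point is a missing specification. Silence still matters, because five mediators and four outcomes give 20 pairs for which the covariates could be chosen after the data are seen.

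A reader might also infer that stable differences will be reported as mediation. The documents do not support that. Such differences alone produce no indirect effect: the arm must shift the mediator and, under the four-step rule, the outcome too. The documents give no expected effect on any mediator, and no correlation or stability for any scale. That these scales persist over time and track the outcomes is plausible, but it is an assumption here.

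Three further limits stand. Percentile bootstrap intervals would give higher error rates (61% rather than 38% at ρ = 0.5, k = 0.7), but the plan names bootstrap standard errors, so those are the rates to use. Time to a first adult visit was not simulated; it has no baseline value, and a visit can precede the 6-month score, which baseline adjustment does not cure. And Section D lists no mediation objective, so Aim 2 is explanatory.

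**Conclusion.** The concern holds as a gap in specification with a foreseeable bias. An analyst who follows Aim 2 literally would fit mediator and outcome models without baselines, and the mediator-outcome path would then be confounded by pre-existing differences. Where the intervention moves both the scale and the outcome by about half an SD, the false-positive rate could be several times the nominal 5%. With smaller effects or weaker correlations it shrinks, in some settings to below 5%. The percentages are illustrative and rest on the assumed correlations, stabilities and arm effects; the direction of the problem does not. Baseline adjustment is clearly better than none, but it reduces the confounding and need not remove it.

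**What to change.** Add to G2, Aim 2: every mediation regression (outcome on arm, mediator on arm, outcome on arm and mediator) includes the baseline score of that mediator and, for HbA1c, adherence and quality of life, the baseline value of that outcome. For time to a first adult visit, include the baseline mediator only. Add that this reduces but may not remove confounding, and that the mediator-outcome association remains observational.

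The cost is a few sentences and up to two more covariates per model. Baseline HbA1c, adherence and quality of life are already needed for the models elsewhere in G2. No new data are needed if the baseline questionnaires contain all five mediator scales; the sponsor should confirm this against the measures attachment.
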